#### 6.4.4. Prior and Concomitant Medications

All medications will be coded using the WHO Drug Global Dictionary, Format B3 [Version SEP 2021 (or a later version if updated during the study)], Anatomical Therapeutic Chemical (ATC) Classification codes.

Prior medications and concomitant medications are defined as follows:

- Prior medications are those taken prior to screening with a stop date and time prior to the start of the Treatment Period.
- Concomitant medications are those with a start date and time on or after the start of the Treatment Period, or those with a start date and time before the start of the Treatment Period and either a stop date and time on or the start of the Treatment Period, or are ongoing at the end of the study.

See Section 5.2.3 for imputation of missing or partial dates for medication.

Prior and concomitant medications will be summarized separately for the ITT population by treatment group and overall for Part A of the study as follows:

CONFIDENTIAL

medication will be presented.

• The number and percentage of subjects with at least one prior / concomitant

CONFIDENTIAL

Protocol Reference: CRD-740-201

• The number and percentage of subjects with at least one prior / concomitant medication within each Anatomical Group (ATC Level 1), Therapeutic Subgroup (ATC Level 2), and preferred term will be presented. The summary will be sorted using numerical counts by descending order of Anatomical Group, then descending order of Therapeutic Subgroup, then descending order of preferred term in the total column. Where groups or terms tie these will be sorted alphabetically.

Prior medications and concomitant medications will be listed separately for the ITT population. In the listings the relative start and stop day of prior / concomitant medication use will be calculated relative to the first dose date and time of treatment and will be presented for those subjects who received at least one dose of treatment. If the concomitant medication is "Ongoing" it will be indicated as such in the listing and the relative stop day will not be calculated. Only original dates will be presented in the listing even though the relative day may be based on an imputed date.

## 6.4.5. Prohibited Concomitant Therapy

Prohibited concomitant therapies are defined as he following drugs taken by subjects from the time of ICF signing onwards:

- PDE-5 inhibitors (ATC codes G04BE03 and G04BE08)
- Known strong inhibitors CYP3A4:
  - o Atazanavir (J05AE08)
  - o Ceritinib (L01ED02)
  - o Clarithromycin (J01FA09)
  - Cobicistat and cobicistat-containing coformulations (V03AX03, J05AR14, J05AR15)
  - o Darunavir (J05AE10, J05AR22, J05AR26)
  - o Idelalisib (L01EM01)
  - o Indinavir (J05AE02)
  - o Itraconazole (J02AC02)
  - o Ketoconazole (D01AC08, D01AC08, H02CA03, J02AB02)
  - Levoketoconazole
  - o Lonafarnib (A16AX20)
  - o Lopinavir (J05AR10)
  - o Mifepristone (G03XB01, G03XB51)
  - o Nefazodone (N06AX06)
  - o Nelfinavir (J05AE04)
  - o Ombitasvir-paritaprevir-ritonavir (J05AP53)

- o Ombitasvir-paritaprevir-ritonavir plus dasabuvir (J05AP52)
- o Posaconazole (J02AC04)
- Ritonavir and ritonavir-containing coformulations (J05AR10, J05AR23, J05AR26, J05AR10, J05AP53, J05AP53)
- o Saquinavir (J05AE01)
- o Telithromycin (J01FA15)
- o Tucatinib (L01EH03)
- o Voriconazole (J02AC03)
- Known strong inducers of CYP3A4:
  - o Apalutamide (L02BB05)
  - o Carbamazepine (N03AF01)
  - o Enzalutamide (L02BB04)
  - o Fosphenytoin (N03AB05)
  - o Lumacaftor (R07AX30)
  - o Lumacaftor-ivacaftor (R07AX30)
  - o Mitotane (L01XX23)
  - o Phenobarbital (N03AA02)
  - o Phenytoin (N03AB02, N03AB05, N03AB04, N03AB54, N03AB52)
  - o Primidone (N03AA03)
  - o Rifampin (rifampicin) (J04AB02, J04AM02, J04AM05, J04AM07, 04AM06)

Prohibited concomitant therapy will be listed for the ITT population.

#### **6.5.** Measurements of Treatment Compliance

Treatment compliance is defined as the number of tablets that were actually taken relative to the number of tablets that should have been taken as per the protocol for the duration of actual treatment exposure.

In general, the percentage compliance, assessed by tablet count, will be calculated as follows:

Compliance (%) =  $\frac{Number\ of\ tablets\ dispensed-Number\ of\ tablets\ returned}{Number\ of\ days\ on\ treatment\ x\ 2\ x\ Number\ of\ tablets/dose} \times 100\%$ 

Number of tablets per dose is mg dosing.

Number of days on treatment will be calculated as follows:

(last dose date of treatment - first dose date of treatment) + 1

The calculated percentage compliance will be categorized as:

CONFIDENTIAL

- < 80% compliance
- $\geq$  80% to  $\leq$  125% compliance
- > 125% compliance

Compliance will be summarized for the SAF by treatment group and overall for Part A of the study as follows:

- Percent compliance will be presented by default summary statistics.
- Number and percentage of subjects within each of the compliance categories will be presented. Any subjects with missing data will be presented as part of a "Missing" category.

In addition, for part A, compliance by period (period 1, period 2, period 3 and pooled periods 2 and 3) will be calculated using the same formula with the denominator (number of days on treatment) corresponding to the number of days within each period. Compliance by period will be summarized in the same way as overall compliance.

Treatment compliance will be listed together with exposure for the SAF. Missing data will not be imputed and only original data for those fields (for example, date fields) will be presented in the listing together with derived variables such as the calculated compliance (%) and exposure duration.

### 6.6. Efficacy Analysis

Efficacy assessments will undergo visit windowing procedure as described in Section 5.1.5 and will be analyzed using analysis visits.

#### 6.6.1. Primary Efficacy Analysis

#### Part A:

The primary endpoint is the change from baseline in plasma cGMP AUC at Week 4. Blood samples for cGMP are collected at Visit 2, Visit 3, Visit 5 and Visit 7 on specific timepoints (pre-dose, 1 hr, 2 hr, 3 hr, 6 hr post dose). AUC0-6 will be derived from those timepoints at each visit using the linear trapezoidal rule.

The change in plasma cGMP AUC0-6 will be compared between CRD-740 and placebo in the mITT population using an analysis of covariance (ANCOVA) model with fixed factors for treatment (2 levels), and Entresto use at baseline (2 levels), and covariates for baseline EF, and baseline plasma cGMP AUC.

The analysis will be repeated on the change from baseline in plasma cGMP AUC at Week 2.

CRD-740 will be analyzed as one treatment group even though CRD-740 consists of two weeks of treatment with CRD-40, followed by two weeks of treatment with CRD-740.

CONFIDENTIAL

The least square means of the change from baseline for each treatment group, along with the 95% confidence intervals (CI), and the least square mean treatment difference and the associated 95% CI for this difference will come from the ANCOVA model.

Observed values and absolute change from baseline at each analysis visit for plasma cGMP AUC will be summarized by treatment group using default summary statistics for continuous variables on the mITT population.

Absolute change from baseline at each analysis visit for plasma cGMP AUC will be plotted by treatment group using mean and standard error for continuous variables on the mITT population.

cGMP data will be listed for mITT population.

#### 6.6.2. Sensitivity Analysis for the Primary Efficacy Endpoints

#### Part A

The following sensitivity analyses of the primary efficacy endpoint will be performed:

- Primary analysis will be repeated on the PP population.
- Primary analysis will be repeated on the Week 2 Analysis population. This analysis will be performed for interim DMC purposes only.
- Primary analysis will be repeated on the Week 4 Analysis population. This analysis will be performed for interim DMC purposes only.
- Change from baseline in log-transformed plasma cGMP AUC over time will be analyzed in the mITT population using a mixed model for repeated measures (MMRM) including treatment, post-baseline visit (Visits 3, 5 and 7), Entresto use, treatment-by-visit interaction, treatment-by-Entresto interaction, visit-by-Entresto use interaction, and baseline EF as a covariate with random effects for subject, intercept, and slope. The covariance structure will be unstructured. No imputation of missing data will be performed. The least-square means of log (plasma cGMP AUC) and associated two-sided 95% CI for each treatment, the estimated least square mean treatment differences (on the log scale), and corresponding two-sided 95% CI coming from the MMRM will be given for all visits.
- The MMRM analysis described above will be conducted on raw plasma cGMP AUC in the mITT population.

CONFIDENTIAL

# 6.6.3. Secondary Efficacy Analysis

#### Part A

[figure not shown]
Not applicable.

# 6.6.4. Sensitivity Analyses for the Secondary Efficacy Endpoints

No sensitivity analyses will be conducted for secondary efficacy endpoints in Part A.

[figure not shown]
# 6.6.5. Subgroup Analysis

Not applicable.

[figure not shown]

CONFIDENTIAL

# 6.7. Safety Analysis

# 6.7.1. Extent of Exposure

Duration of exposure will be defined in week as:

Exposure (weeks) = ([date of last dose - date of first dose]) / 7

The calculated exposure duration of exposure will be categorized for Part A as:

- Less or equal than 2 weeks
- > 2 weeks to 4 weeks
- > 4 weeks to 12 weeks

## • > 12 weeks

Duration of exposure will be summarized in two ways for the SAF by treatment group and overall for Part A of the study.

- Descriptive statistics will be presented for duration of exposure.
- Number and percentage of subjects within each of the exposure categories will be presented.

A listing of overall treatment exposure data, including the first and last dates of treatment will be presented together with compliance for the SAF. Further, study treatment administration data will be listed for the SAF.

#### 6.7.2. Adverse Events

All AEs recorded on the eCRF will be coded using the MedDRA dictionary [version 24.1 or a later version if updated during the study] and classified as either pre-treatment AEs or treatment—emergent AEs (TEAEs) as follows:

- Pre-treatment AEs are events that start prior to the start of the Treatment Period.
- TEAEs are either events with start date and time after the first study treatment administration or events with start date and time prior to the first study treatment administration whose severity worsening or becoming serious after the start of the Treatment Period.
- The relationship between a TEAE and treatment is assessed as related, or not related. A treatment-related TEAE will be defined as a TEAE considered by the investigator as related to treatment or unknown / missing relationship to treatment.
- The severity of and AE is assessed as Mild / Moderate / Severe according to the investigator. Severe TEAEs are defined as TEAEs assessed as being "Severe" and includes those events where the severity is missing.
- TEAEs leading to discontinuation of study are defined as TEAEs where "Required Withdrawal from study" is indicated as other action taken on AE eCRF form.
- TEAEs leading to discontinuation of study treatment are defined as TEAEs where "Drug Withdrawn" is indicated as action taken with study treatment on AE eCRF form
- TEAEs leading to dose interruption are defined as TEAEs where "Drug Interrupted" is indicated as action taken on AE eCRF form

For Part A, the primary safety analysis will be performed by reporting the exposure-adjusted incidence rates in subject-years for AE and SAE defined as the number of subjects with that particular AE or SAE within a system organ class or preferred term during the relevant period divided by the sum of the at-risk times. For a subject who does not have that particular AE or SAE, the at risk time is the exposure time in each period in years. For a subject who does have

CONFIDENTIAL

that particular AE or SAE, the at risk time is the exposure time until the event occurs in each period in years. The adjusted incidence rates will be presented by system organ class and preferred term for Period 1, and separately for Periods 2 and 3 combined. The Hodges-Lehmann methodology will be used to estimate the within-subject point and interval treatment difference.

Adverse events will be summarized by treatment group and overall by dose period (Period 1, Period 2, Period 3, pooled Period 2 and Period 3, and overall) for Part A in the SAF.

- An overview of TEAEs including the number and percentage of subjects with at least one of each mentioned TEAE type:
  - o Any TEAE
    - Leading to discontinuation of study
    - Leading to discontinuation of study treatment
    - Leading to death
    - Mild
    - Moderate
    - Severe
  - Any study treatment related TEAE
    - Leading to discontinuation of study
    - Leading to discontinuation of study treatment
    - Leading to death
  - o Any serious TEAE
    - Leading to discontinuation of study
    - Leading to discontinuation of study treatment
    - Leading to death
  - o Any serious study treatment related TEAE
    - Leading to discontinuation of study
    - Leading to discontinuation of study treatment
    - Leading to death
- The number and percentage of subjects reporting each TEAE and the count of number of events will be summarized by SOC and PT for the following types of TEAEs:
  - o All TEAEs
  - o TEAEs Leading to Discontinuation of Study Treatment
  - o TEAEs Leading to Dose interruption
  - o TEAEs Leading to Study Withdrawal
  - TEAEs Leading to Death
  - o TEAEs by Maximum Severity
  - o TEAEs by Relationship to Treatment
  - o TEAEs by Relationship and Maximum Severity
  - Study Treatment related TEAEs
  - Study Treatment Related TEAEs Leading to Discontinuation of Study Treatment

CONFIDENTIAL

- CONFIDENTIAL
  Protocol Reference: CRD-740-201
- o Study Treatment related TEAEs Leading to Death
- Serious TEAEs
- o Serious TEAEs Leading to Discontinuation of Study Treatment
- o Serious TEAEs Leading to Dose Interruption
- Serious TEAEs Leading to Study Withdrawal
- Serious TEAEs Leading to Death
- Study Treatment Related Serious TEAEs
- Study Treatment Related Serious TEAEs Leading to Discontinuation of Study Treatment
- o Study Treatment Related Serious TEAEs Leading to Death
- o Study Treatment Related Serious TEAEs Leading to Study Withdrawal
- The number and percentage of subjects who died will be summarized by the primary reason of death (if available)

In the above summaries, subjects with more than one TEAE within a particular SOC are counted only once for that SOC. Similarly, subjects with more than one TEAE within a particular PT are counted only once for that PT.

For summaries by maximum severity, subjects with multiple TEAEs within a particular SOC or PT will be counted under the category of their most severe TEAE within that SOC or PT.

Summaries by SOCs and PTs will be sorted by SOCs by their Internationally Agreed Order (MedDRA) and PTs within SOC by descending order of total incidence. Where preferred terms tie PTs will be sorted alphabetically.

No statistical comparisons of AEs between treatment groups will be performed.

All AE data will be listed and Pre-treatment AEs and TEAEs will be presented together. Treatment-emergence status will be flagged in the listing. The listing will present the relative start and stop day of the AE calculated relative to the first dose of treatment and will be presented for those subjects who received at least one dose of treatment. If the AE is "Ongoing" it will be indicated as such in the listing and the relative stop day will not be calculated. Only original dates will be presented in the listing even though the relative day may be based on an imputed date.

In addition, the following listings will be presented:

- Listing of Deaths
- Listing of Serious TEAEs
- Listing of Severe TEAEs
- Listing of AEs Leading to Interruption of Study Treatment
- Listing of AEs Leading to Discontinuation of Study Treatment
- Listing of AEs Leading to Study Withdrawal

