8.5. Safety Analysis

All safety data will be summarized, by treatment group and dose period (Period 1, Period 2, Period 3, pooled Period 2 and Period 3, and overall) for Part A and by treatment group for Part B in the Safety Data Set.

For Part A, the primary safety analysis will be performed by reporting the exposure-adjusted incidence rates in subject-years for AE and SAE defined as the number of subjects with that particular AE or SAE within a system organ class or preferred term during the relevant period divided the sum of the at-risk times. The total at risk time is the sum of exposure time in each period in years. The adjusted incidence rates will be presented by system organ class and preferred term for Period 1, and separately for Periods 2 and 3 combined. The Hodges-Lehmann methodology will be used to estimate the within-subject point and interval treatment difference.

FINAL 10 AUG 2022 Page 56 of 73

Adverse events

For both Part A and Part B, global incidence of emergent adverse events (EAE) (i.e., all events occurring, worsening or becoming serious after the first study treatment intake) will be given by system organ class and preferred term according to the Medical Dictionary of Regulatory Activities.

The same description will be performed for serious EAE, severe EAE, treatment related EAE, and EAE leading to study drug withdrawal.

AEs leading to death will also be summarized.

Vital signs / Physical examination

For both Part A and Part B, descriptive statistics will be performed on observed values at each visit and on each change and relative change from baseline.

Box plots will be produced for some pre-selected vital signs.

ECG abnormalities

For both Part A and Part B, quantitative routine 12-lead ECG results will be summarized on observed values at each visit and on each change and relative change from baseline.

Box plots will be produced for some pre-selected ECGs.

12-lead ECG data interpretations and quantitative values will be listed.

Laboratory tests

For both Part A and Part B, descriptive statistics will be performed on observed values at each visit and on each change and relative change from baseline.

The number and percentage of subjects having a value out of reference laboratory range (respectively out of potentially clinically significant range) will also be provided.

Box plots will be produced for some pre-selected lab parameters.

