Appendix 1 – Adverse Event Definitions

Definitions

An adverse event (AE) is any untoward medical occurrence associated with the use of a drug in humans, whether or not considered drug related. This includes the following:

- Any clinically significant worsening of a pre-existing condition.
- Any recurrence of a pre-existing condition.
- An AE occurring from overdose of a sponsor study drug whether accidental or intentional (i.e., a dose higher than that prescribed by a health care professional for clinical reasons).
- An AE occurring from abuse of a sponsor study drug (i.e., use for non-clinical reasons).
- An AE that has been associated with the discontinuation of the use of a sponsor study drug.

Note: A procedure is not an AE, but the reason for a procedure may be an AE.

A pre-existing condition is a clinical condition (including a condition being treated) that is diagnosed before the subject signs the informed consent form and that is documented as part of the subject's medical history.

The questions concerning whether the condition existed before the start of the active phase of the study and whether it has increased in severity and/or frequency will be used to determine whether an event is a treatment-emergent AE. An AE is considered to be treatment-emergent if (1) it is not present when the active phase of the study begins and is not a chronic condition that is part of the subject's medical history, or (2) it is present at the start of the active phase of the study or as part of the subject's medical history, but the severity or frequency increases during the active phase. The active phase of the study begins at the time of the first dose of the study drug. The active phase of the study ends at the follow-up visit.

Reporting of Adverse Events

At each visit, the investigator, or delegate, will determine whether or not any AEs have occurred. Non-leading questions such as "How are you feeling today?" or "Have you had any health concerns since your last visit?" should be used to elicit the subject (or, when appropriate, from a caregiver, surrogate, or the subject's legally authorized representative) to report any possible AEs. If any AEs have occurred, they will be recorded in the AE section of the electronic case report form (eCRF) and in the subject's source documents. If known, the diagnosis should be recorded, in preference to listing the individual signs and symptoms.

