AE reporting begins from the time of informed consent and ends 28 days after the last dose of study drug.

FINAL 10 AUG 2022 Page 60 of 73

Assessment of Severity

The investigator will be asked to provide an assessment of the severity of the AE using the following categories:

- **Mild**: Usually transient and may require only minimal treatment or therapeutic intervention. The event does not generally interfere with usual activities of daily living.
- **Moderate**: Usually alleviated with additional specific therapeutic intervention. The event interferes with usual activities of daily living, causing discomfort but poses no significant or permanent risk of harm to the subject.
- **Severe**: Interrupts usual activities of daily living, significantly affects clinical status, or may require intensive therapeutic intervention.

Relationship to Study Drug

The investigator will make a determination of the relationship of the AE to the study drug using a binary system according to the following guidelines:

- **Related**: There is a reasonable possibility that the drug causes the AE.
- **Not related**: There is no reasonable possibility that the drug causes the AE.

Action Taken for Adverse Events

The investigator or his/her designee will record the action taken for the AE in the eCRF. Actions taken will include:

- **Dose not changed**: The medication schedule was not changed.
- **Drug interrupted**: The medication schedule was modified by temporarily terminating the prescribed regimen of medication.
- **Drug withdrawn**: The medication schedule was modified through termination of the prescribed regimen of medication.
- Not applicable
- Unknown

Follow-up of Adverse Events

All AEs or serious adverse events (SAEs) that are ongoing at the time of discontinuation, or that develop prior to the final follow-up visit, will be followed for 28 days, or until resolution or stabilization.

FINAL 10 AUG 2022 Page 61 of 73

Adverse Drug Reactions

All noxious and unintended responses to an investigational medicinal product (IMP; i.e., where a causal relationship between an IMP and an AE is a reasonable possibility) related to any dose should be considered adverse drug reactions.

For marketed medicinal products, a response to a drug which is noxious and unintended and which occurs at doses normally used in man for prophylaxis, diagnosis, or therapy of diseases or for modification of physiological function is to be considered an adverse drug reaction.

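### SAP 6.7.2 leaves out the increase-in-frequency criterion for treatment-emergent AEs that Protocol Appendix 1 contains, and SAP section 7 does not declare the change

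*SAP*

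**What the plan says.** Three places define when an adverse event is treatment-emergent, and they do not match.

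- **SAP 6.7.2** has two branches. The first covers new onset: "TEAEs are either events with start date and time after the first study treatment administration". The second covers events that began earlier, and admits only those "whose severity worsening or becoming serious after the start of the Treatment Period". Everything else with early onset falls under the companion rule: "Pre-treatment AEs are events that start prior to the start of the Treatment Period".
- **Protocol Appendix 1** counts an event that was present when the active phase began, or was part of the medical history, "but the severity or frequency increases during the active phase".
- **Protocol 8.5**, the safety analysis section, defines emergent events as "all events occurring, worsening or becoming serious after the first study treatment intake". It names neither severity nor frequency as the measure of worsening.

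SAP section 7 lists several departures from the protocol, including the cGMP baseline and the removal of the accumulation ratios. The TEAE definition is not among them.

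**The concern.** Safety and tolerability is a primary objective of Part A, and the SAP's AE count tables are built on TEAEs. Events can be open at first dose because, under Appendix 1, "AE reporting begins from the time of informed consent and ends 28 days after the last dose of study drug". An intermittent symptom that starts in screening and becomes more frequent on treatment, with no change of grade, is treatment-emergent under Appendix 1 and pre-treatment under the SAP.

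A more frequent mild symptom is one way in which poor tolerability can show itself. A rule that looks only at severity and seriousness misses it. Because the change is not declared, a reader of the study report would have no reason to suspect that the tables use a narrower definition than the protocol's appendix.

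**Working it through.** The plan gives no figure to reproduce, so the check is mainly a comparison of texts.

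**Step 1. What turns an event with onset before first dose into a TEAE?**

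| Trigger after dosing starts | SAP 6.7.2 | Protocol Appendix 1 | Protocol 8.5 |
|---|---|---|---|
| Severity increases | yes | yes | yes, as worsening |
| Frequency increases | no | yes | not named; unqualified worsening can include it |
| Becomes serious | yes | not named | yes |

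The SAP drops one trigger that Appendix 1 has and adds one that Appendix 1 lacks. Against 8.5, it narrows worsening to severity.

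**Step 2. Can such events exist?** The Part A Schedule of Assessments puts screening at Day -15 to Day -2, and its footnote accepts up to 21 days in rare situations. Consent is taken in that window, so the interval before first dose is short and varies between subjects. Appendix 1 grades severity in three broad categories, so a symptom can become more frequent and keep its grade.

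**Step 3. A hypothetical case.** Mild intermittent dizziness starts on Day -7, occurs weekly before dosing and daily from Day 5, and stays mild. It is held as one record. Under Appendix 1 it counts as 1. Under SAP 6.7.2 the onset is before dosing, severity is unchanged and it is not serious, so it counts as 0.

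**Step 4. Where does it go missing?**

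- The overview and the SOC and preferred-term summaries in SAP 6.7.2 are TEAE-based, so it is absent.
- The AE categories in the DMC safety profile (SAP 6.7.7) are TEAE categories, so it is absent there too.
- The AE listing shows pre-treatment and emergent events together with an emergence flag, so it remains visible.
- The exposure-adjusted rates are worded for AEs and SAEs, not TEAEs. For a subject with the event, at-risk time runs until the event occurs, which has no clear meaning when onset precedes exposure. Its inclusion there is undetermined.

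**Step 5. Scale.** Inputs: about 60 subjects (Protocol 8.1) and 2:1 allocation (Protocol 5.3).

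- CRD-740: 60 × 2/3 = 40, so one subject is 1/40 = 2.5 percentage points.
- Placebo: 60 × 1/3 = 20, so one subject is 1/20 = 5 percentage points.

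The documents do not say how many subjects will have an AE open at first dose, or how many of those AEs will rise in frequency alone. The total therefore cannot be computed.

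**The case against.** The strongest reply is that the protocol is itself divided. Section 8.5 does not mention frequency, and the SAP follows it closely, including the seriousness trigger. This stands in part: some of the inconsistency lies inside the protocol, and editing the SAP alone would not remove it. It does not clear the SAP, because 8.5 does not limit worsening to severity and the SAP does.

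A second reply is that Appendix 1 already makes the worsening an event in its own right, since its AE definition includes "Any clinically significant worsening of a pre-existing condition" and "Any recurrence of a pre-existing condition". Entered as a new record after dosing, such an event is a TEAE under the SAP's first branch. This holds for conditions in the medical history. But Appendix 1 defines a pre-existing condition as one diagnosed before consent was signed, so the provision does not reach an AE that began between consent and first dose. Neither document tells sites to open a new record when such an AE becomes more frequent. Some may do so, and the eCRF is not available to settle it.

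A third reply is that severity is graded partly by interference with daily activities, so a marked rise in frequency may raise the grade and be caught anyway. This is fair and reduces the number of cases, but does not bring it to zero.

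A reader might also infer more than the documents support:

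- **That every event rising in frequency is lost from all safety output.** Worsening of a pre-consent condition can be recorded afresh and counted, the AE listing keeps the rest, and the exposure-adjusted rates are not clearly restricted to TEAEs.
- **That the SAP rule can only remove events.** Relative to Appendix 1 it also adds those that become serious.
- **That the safety comparison is biased towards no harm.** That requires the drug to raise symptom frequency, for which the documents give no evidence. SAP 6.7.2 also rules out statistical comparisons of AEs between treatment groups.

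**Conclusion.** The discrepancy is real and undeclared, and its reach is narrow. It affects AEs held as a single record, with onset between consent and first dose, that become more frequent on treatment without a change of grade or seriousness. These are left out of the TEAE summaries and the TEAE items for the DMC.

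The number is probably small, because the onset window is short and several conditions must hold together. That is a judgement, since the documents supply no rates. The per-subject shift of 2.5 points on CRD-740 or 5 on placebo assumes that 60 subjects are randomized exactly 2:1 and all are dosed. This is a minor point of definition, worth correcting because safety is a primary objective and the correction is cheap.

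**What to change.** Reword the second branch in SAP 6.7.2 so that an event with onset before first dose is treatment-emergent if, once the Treatment Period has begun, its severity or its frequency increases or it becomes serious. Align Protocol 8.5 and Appendix 1 to that same definition, so that all three places name severity, frequency and seriousness.

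If the eCRF does not capture frequency, carry out a blinded review of AEs ongoing at first dose before database lock, with queries to sites, and flag those that became more frequent. If the sponsor prefers the narrower rule, it should be declared and justified in SAP section 7, and the protocol's two definitions still need reconciling.

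The cost is one phrase in the SAP, matching wording in the protocol and a short review of what should be few records. Reported TEAE counts may rise slightly.
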